December 10, 2025

RESEARCH PROTOCOL FOR THE PROJECT

FOSTERING UKRAINE'S CAPACITY IN DELIVERY AND RESEARCH OF INNOVATIVE EVIDENCE-BASED PTSD TREATMENT

SECTION 1: PROJECT

Title:	Fostering Ukraine's capacity in delivery and research of innovative evidence-based PTSD treatment
Acronym:	Lux4UA

Applicant(s):

Researcher/Student	Name:	[name]
	Position at UL:	Research scientist
	Faculty / IC:	FHSE
	Research Unit:	Department of Behavioural and Cognitive Sciences
	Telephone no:	([contact]
	Email:	[contact]

Principal Investigator	Name:	[name]
	Position at UL:	Research scientist
	Faculty / IC:	FHSE
	Research Unit:	Department of Behavioural and Cognitive Sciences
	Telephone no:	([contact]
	Email:	[contact]

Funding:

Source:	FNR under LUXAID BRIDGES CALL
---------	--------------------------------------

SECTION 2: SHORT SUMMARY OF THE PROJECT

(including research design and methodology)

The Lux4UA Project's goal is to foster Ukrainian mental health professionals' capacity in transdisciplinary research on innovative, evidence-based trauma treatment (Reconsolidation of Traumatic Memories (RTM) Protocol) in humanitarian emergencies due to war and displacement. To accomplish this goal, the RTM Protocol Effectiveness and Feasibility studies will be conducted.

The RTM Protocol effectiveness study implies a randomised field trial comparing RTM with treatment-as-usual (Trauma-Focused Cognitive Behavioral Therapy (TF-CBT), Eye Movement Desensitization and Reprocessing (EMDR), or pharmacotherapy) across three customary clinical settings in Ukraine (hospital in-patient, hospital out-patient, private psychotherapy). The primary outcome is the loss of Post-Traumatic Stress Disorder (PTSD) diagnosis or change in symptoms; secondary outcomes include depression and anxiety at post-treatment, 6 m and 12 m follow-up.

Objective 1: *To compare the effectiveness of the RTM Protocol for the treatment of trauma-related mental conditions with other evidenced-based trauma-focused therapies (TF-CBT, EMDR and medication).*

Objective 2: *To investigate the effectiveness of the RTM Protocol for the treatment of trauma-related mental conditions in different settings of mental health (MH) care (inpatient and outpatient hospital care for veterans and private psychotherapy for civilians)*

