Study 2: The RTM Protocol and Training feasibility study	To analyse the acceptability of the RTM Protocol among MH professionals and persons with PTSD and the adaptability of the RTM Protocol & RTM Training for the country context.	 Human participants  Vulnerable population  Human biological material  Pre-collected biological material  Personal data  Pre-collected personal data  risks on the environment  risks on the society

Please expand the rows in case of additional studies.

SECTION 4: DETAILS OF EACH STUDY

Study 1: The RTM Protocol Effectiveness Study

Target sample size: (Please justify the target sample size, either statistically or by referring to existing literature)	
The research sample for the EFFECTIVENESS STUDY is expected to be 120 participants (people with PTSD), approximately equally distributed between experimental and control groups (at least 20 participants).
 
The sample expectancy is based on case numbers estimated by every MH care provider involved in the Project. The allocation ratio was calculated based on the assumption that the mean of PCL-5 would be 25.0 for the control group and 21.0 for the experimental group (SD of 3.0); a type 1 risk is 5.0%, and a type 2 risk is 20.0%, for the bilateral test and a dropout rate at 20.0%, the minimum N of participants in each group should be equal to 12.

Key inclusion criteria:	Key inclusion criteria for the effectiveness study participants are (1) being adults \geq 18 years, (2) having a diagnosis of PTSD determined by DSM-5-TR or ICD-11 and/or (3) having PTSD symptoms causing clinically significant distress or impact on social, occupational, or other areas of functioning defining on base of using PTSD Checklist PCL-5, (4) being resident of Ukraine.
Key exclusion criteria:	Key exclusion criteria for the effectiveness study participants are (1) having any other acute comorbid mental health conditions, (2) receiving any other parallel PTSD treatment, (3) being unable to provide informed consent, has severe cognitive impairment, or is otherwise unlikely to adhere to study procedures.
Age range of participants:	Adults aged 18-65.
Country/ies of recruitment:	Ukraine

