Expected duration of procedure:	Data collection will occur at baseline (diagnostic session), 1 month after complete treatment application, in 6 months (follow-up booster session), and in 12 months (second follow-up booster session) and will take approximately 15 min each, 45 min per person.
Data Collection:	
Paper questionnaires, digital entry; no audio/video.
 
Data on age, gender, veteran and IDP statuses, residency, type of trauma, medical diagnosis and symptoms, scores from PCL-5 (for PTSD), PHQ-9 (for depression), GAD-7 (for anxiety) diagnostic scales will be collected from printed questionnaire sheets filled in by participants.
 
PTSD diagnosis will be collected from medical records.
 
Names, email-address, phone number will be collected from printed informed consent.
 
Data transfer. Aggregated, fully anonymised raw data will be shared by implementing partners' coordinators through Zenodo under closed access and using the EUSurvey Platform (an online survey-management

	
system developed by the European Commission) only with PI [name].

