Methodology:	
Research design. The RTM Protocol effectiveness study implies a randomised field trial comparing RTM with treatment-as-usual (TF-CBT, EMDR or pharmacotherapy). It is chosen and will be standardised based on CONSORT 2010 Statement: reporting parallel group randomised trials. To enhance the external validity of the findings, all the interventions are planned to be explored among three different settings of mental health care accustomed to Ukraine: mental health hospital care (inpatient and outpatient care for veterans) and psychotherapeutic practice (for civil trauma survivors).
 
Measures. Primary outcome effectiveness measures are MH professional proved existence or loss of PTSD diagnosis and/or PTSD symptoms severity measured by PTSD Checklist PCL-5 (re-experiencing of trauma, avoidance of trauma-related stimulus, negative alterations in cognition and mood, hyper-arousal).
 
Among secondary outcome measures will be the existence and severity of depression and anxiety-related symptoms according to PHQ-9 and GAD-7 scales.
 
Data analysis. Descriptive Statistics: means, SDs, medians, frequencies and percentages, baseline comparability between groups (t-tests, chi-square tests). Primary and Secondary Outcome Analysis: mixed-effects repeated measures ANOVA. Handling Missing Data: multiple imputation or maximum likelihood estimation under MAR assumption. Effect Size Reporting: Cohen's d, odds ratios, and 95% confidence intervals.
 
Data collection will be in Ukrainian language (all the scales are validated in Ukrainian and recommended by the World Health Organisation for the screening of the mentioned mental health conditions) at baseline (diagnostic session), 1 month after complete treatment application, in 6 months (follow-up booster session), and in 12 months (second follow-up booster session).

Study 2: The RTM Protocol and Training Feasibility Study

Target sample size: (Please justify the target sample size, either statistically or by referring to existing literature)	
The research sample for the FEASIBILITY STUDY is expected to be 20 participants according to the trauma-related cases/workforce availability ratio of implementing partners: 10 persons from each site.
 
The number of clients is expected to be 60 persons (persons treated with the RTM Protocol) according to the RTM Protocol effectiveness study description.

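### The primary outcome is left as an open choice between loss of PTSD diagnosis and PCL-5 severity, with no rule for which decides the trial; the sample-size calculation and the named model fit only PCL-5

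*Protocol*

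**What the plan says.** **Primary outcome.** The Section 2 summary states: "The primary outcome is the loss of Post-Traumatic Stress Disorder (PTSD) diagnosis or change in symptoms". The Methodology row of Section 4, Study 1, states it as "MH professional proved existence or loss of PTSD diagnosis and/or PTSD symptoms severity measured by PTSD Checklist PCL-5". The connectors differ, and neither place ranks the two measures.

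**Sample size.** The Target sample size row of Section 4, Study 1, says of the 120: "The sample expectancy is based on case numbers estimated by every MH care provider involved in the Project". The one calculation given assumes that "the mean of PCL-5 would be 25.0 for the control group and 21.0 for the experimental group (SD of 3.0", with a two-sided 5% type 1 risk, a 20% type 2 risk and 20% dropout, and arrives at a minimum of 12 per group. It gives no rate for loss of diagnosis.

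**Analysis.** The Methodology row assigns a mixed-effects repeated measures ANOVA to primary and secondary outcomes alike. Odds ratios appear in the list of effect sizes to be reported.

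**Diagnosis.** Entry requires "having a diagnosis of PTSD determined by DSM-5-TR or ICD-11 and/or (3) having PTSD symptoms causing clinically significant distress". The source is stated: "PTSD diagnosis will be collected from medical records".

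**Timing.** The Expected duration row says: "Data collection will occur at baseline (diagnostic session), 1 month after complete treatment application", followed by 6 and 12 months. Section 6, Study 1, puts the first follow-up at 2 weeks and lists PCL-5, PHQ-9 and GAD-7 for the follow-up assessments. It does not mention diagnostic status there.

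**The concern.** A primary outcome exists so that one pre-stated result decides the trial. Here two different variables, a professional's yes/no diagnosis and a questionnaire score, share that role without a rule. The wording allows three readings: either measure suffices, both are needed, or one will be chosen. They carry different error rates and different power.

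Under the first reading, the single 5% type 1 risk in the sample-size row does not hold for the main claim. Under the second, the trial turns on the measure for which the protocol has made no planning assumption. The third leaves room to choose after results are known, unless another document closes it first.

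The rest of the plan is built for one measure only. The calculation uses PCL-5 means, and a repeated measures ANOVA is a model for a score, not for a binary status. Two smaller points add to this. Collection of diagnostic status at follow-up is not explicit. Because the diagnosis and symptom criteria are joined by *and/or*, some participants may also enter with no diagnosis to lose.

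**Working it through.** **1. The plan's own figure.** Inputs (Section 4, Study 1, Target sample size): means 25.0 and 21.0, so a difference of 4.0; SD 3.0; two-sided 5%; power 80%; dropout 20%.

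n per group = 2 × (1.960 + 0.842)² × (3.0/4.0)² = 2 × 7.85 × 0.5625 = 8.83, rounded up to 9. Allowing for dropout: 9/0.80 = 11.25, rounded up to 12. The stated 12 reproduces. (A t-based calculation needs 10 evaluable, and 10/0.80 = 12.5, so 13.) Only PCL-5 quantities enter.

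**2. Reading A: a win on either measure counts, each tested at two-sided 5%.** Under no effect on either measure,

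false-positive rate = 1 − P(|Z₁| < 1.96 and |Z₂| < 1.96), with (Z₁, Z₂) bivariate normal with correlation ρ.

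If independent: 1 − 0.95² = 0.0975.

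| ρ (assumed) | False-positive rate |
|---|---|
| 0 | 9.75% |
| 0.5 | 9.07% |
| 0.7 | 8.35% |
| 0.9 | 7.04% |

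The documents give no correlation. Zero is the upper figure in this table and is implausible for two measures of the same disorder in the same people. Every value shown exceeds 5%.

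**3. Reading B: both must succeed.** Type 1 error stays at or below 5%. For power, Section 6 plans 3 settings × 20 = 60 per arm, and 60 × 0.80 = 48 completers.

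PCL-5: 4.0 / (3.0 × √(2/48)) = 4.0/0.612 = 6.53, and 6.53 − 1.96 = 4.57, so power is above 99.9%.

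With one component almost certain to succeed on the plan's assumptions, power for both is essentially the power for loss of diagnosis. The protocol gives no rate from which to compute that. For illustration only, with **assumed** rates, 48 per arm, settings pooled and a two-sided 5% test of two proportions:

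| Assumed loss of diagnosis (the two arms) | Power |
|---|---|
| 30% and 50% | 51.6% |
| 40% and 60% | 50.0% |
| 50% and 70% | 51.6% |
| 30% and 60% | 85.1% |
| 40% and 70% | 85.1% |
| 50% and 80% | 88.1% |

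The answer runs from about 50% to 88% depending on an assumption the plan does not make.

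**4. Reading C: two primaries with the 5% split equally (2.5% each).** PCL-5 part: 2 × (2.241 + 0.842)² × 0.5625 = 10.69, so 11 evaluable, and 11/0.80 = 13.75, so 14 per group. This is well within 60 per arm, so a split costs the PCL-5 part little.

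**The case against.** The strongest reply is that only the protocol is at hand. A statistical analysis plan may name the binary model, the analysis set and any division of the 5%, and listing odds ratios beside Cohen's *d* shows that a binary analysis was foreseen. That stands for the modelling detail. It does not answer the main point, because the protocol itself states the primary outcome, and states it as an alternative. For the same reason a reader might infer that the outcome will be picked after the data are seen. The wording permits that, but the document does not show it, since a later plan could settle the matter first.

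It can also be said that naming a single visit is not obligatory: a group effect over the scheduled visits is a legitimate primary contrast. That is right. What is needed is that the contrast be stated.

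A reader might infer that loss of diagnosis has no criterion or schedule at all. That goes too far. The inclusion criteria name DSM-5-TR or ICD-11 (for entry, without choosing between them), Section 4 names the confirmer and the source, and there is a general data-collection schedule. The fair statement is that follow-up collection of diagnostic status is not explicit.

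Finally, making PCL-5 the primary outcome is partly a preference. It is completed by participants, whereas diagnosis is professionally confirmed and is named first. This also stands, so the correction should allow either choice.

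**Conclusion.** The point holds. The protocol does not fix which of two measures decides the trial, and its calculation and named model serve only one of them. If either measure suffices at an unadjusted 5%, the false-positive rate is about 7.0% to 9.1% at assumed correlations of 0.9 to 0.5, with 9.75% as the independence figure. If both are required, there is no inflation, and power rests on loss of diagnosis, which the document gives no means to compute.

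Three stronger conclusions are not supported. The minimum of 12 per group is not an arithmetical error. The trial cannot be called underpowered for loss of diagnosis, because that depends wholly on assumed rates. Nor does multiplying two 80% powers describe the both-required reading, since PCL-5 power at the planned size is above 99.9% on the plan's assumptions. The point about participants without a diagnosis is only a possibility: the sample-size row describes the 120 as people with PTSD.

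**What to change.** In Sections 2 and 4, replace *or* and *and/or* with one named primary outcome. Alternatively keep two, and state whether both must succeed or how the 5% is divided between them.

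PCL-5 severity is the option the plan supports best, because it has the sample-size assumptions and fits the named model. If it is chosen, state which score is meant (the sample-size row does not say it is the total) and the deciding contrast: a named visit, or the group effect over the scheduled visits. The first follow-up must be reconciled in either case (1 month in Section 4, 2 weeks in Section 6). If loss of diagnosis is chosen or kept as a second primary, add the assumed rates and a calculation for it.

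Whether it is primary or secondary, analyse loss of diagnosis with a binary-outcome model, for example logistic regression, which yields the odds ratio already listed. Do so among participants with a recorded PTSD diagnosis at baseline, with status recorded at a stated visit.

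The cost is wording in Sections 2 and 4 and a diagnostic-status entry at follow-up. With PCL-5 as sole primary, the planned 120 is unaffected. The downside is that a result on the outcome not chosen can no longer be claimed as primary success.

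### One linear model, a repeated measures ANOVA, is assigned to yes/no outcomes too, although the plan promises odds ratios with 95% CIs that it does not estimate

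*Protocol*

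**What the plan says.** All references are to the Protocol.

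- **Model.** Section 4, Study 1, Methodology, Data analysis: "Primary and Secondary Outcome Analysis: mixed-effects repeated measures ANOVA". It does not split outcomes by type. Chi-square tests appear only for baseline comparability. No logistic, GEE or generalised linear mixed model is named for Study 1.
- **Effect measures.** The same paragraph lists Cohen's d, "odds ratios, and 95% confidence intervals".
- **Missing data.** The same paragraph: "multiple imputation or maximum likelihood estimation under MAR assumption".
- **Primary measures.** Section 4, Study 1, Measures: "MH professional proved existence or loss of PTSD diagnosis and/or PTSD symptoms severity". The Section 2 summary words it differently: "The primary outcome is the loss of Post-Traumatic Stress Disorder (PTSD) diagnosis or change in symptoms".
- **Secondary measures.** Section 4, Study 1, Measures: "existence and severity of depression and anxiety-related symptoms according to PHQ-9 and GAD-7 scales".
- **Who has a diagnosis at entry.** Section 4, Study 1, Key inclusion criteria: "having a diagnosis of PTSD determined by DSM-5-TR or ICD-11 and/or (3) having PTSD symptoms". Some participants may therefore enter on symptoms without a diagnosis.
- **Source of the diagnosis.** Section 4, Study 1, Data Collection: "PTSD diagnosis will be collected from medical records".

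**The concern.** The list of outcomes mixes scores with yes/no states. A repeated measures ANOVA suits the scores, and Cohen's d goes with them. The odds ratios can only belong to the yes/no states, and for these the one model named works on another scale. The model and the effect measure disagree within a single paragraph.

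What is at stake is pre-specification. Several routes lead to an odds ratio for loss of diagnosis, and they give different numbers from the same data. With none fixed, the choice could be made after the results are seen, for a measure that the Section 2 summary names first.

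There is also a smaller misfit. Among participants diagnosed at entry, the diagnosis is present in everyone at baseline. It has no variance there, so a repeated measures ANOVA that takes baseline as one of its response levels describes this outcome poorly.

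**Working it through.** **1. The plan's own figure.** Section 4, Study 1, Target sample size assumes PCL-5 means of 25.0 and 21.0, SD 3.0, two-sided 5%, 80% power and 20% dropout.

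n = 2 × [3.0 × (1.960 + 0.842) / 4.0]² = 8.83, so 9 per group; 9 / 0.80 = 11.25, so 12.

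The stated minimum of 12 reproduces. It rests on a comparison of score means alone. The protocol gives no rate for loss of diagnosis, so every rate below is an assumption.

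**2. What the named model estimates on 0/1 data.** The arm effect at a visit is p1 − p0. The odds ratio is OR = [p1/(1 − p1)] / [p0/(1 − p0)].

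| Assumed rates | Difference | Odds ratio |
|---|---|---|
| 40% vs 60% | 20 points | (0.6/0.4)/(0.4/0.6) = 2.25 |
| 70% vs 90% | 20 points | (0.9/0.1)/(0.7/0.3) = 3.86 |

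The same ANOVA effect corresponds to different odds ratios. Fitted proportions allow a crude odds ratio to be computed, but the model's coefficient and interval are not an odds ratio with a CI.

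**3. The simple route outside the named model.** A 2×2 table at one visit does give an interval. Take 60 per arm less 20%, so 48, at 40% vs 60%:

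SE(log OR) = √[1/(48 × 0.4 × 0.6) + 1/(48 × 0.6 × 0.4)] = 0.417

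95% CI = exp(0.811 ± 1.96 × 0.417) = 0.99 to 5.09

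A logistic model with arm alone at that visit gives the same interval. Neither is the stated analysis, and neither uses the repeated measures or the likelihood-based missing-data handling.

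**4. Why naming the model matters even on the odds scale.** In a logistic model with a participant random intercept of SD σ and no covariates, the arm proportion is p = ∫ expit(a + σz) φ(z) dz. Solving for 40% and 60% gives a = −0.490 and +0.490 (σ = 1.0), ∓0.572 (σ = 1.5) and ∓0.668 (σ = 2.0). The subject-specific odds ratio is exp(2|a|):

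| Assumed σ | Population-averaged OR | Subject-specific OR |
|---|---|---|
| 1.0 | 2.25 | 2.66 |
| 1.5 | 2.25 | 3.14 |
| 2.0 | 2.25 | 3.80 |

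Both columns describe the same 40% vs 60% result.

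**5. Scores: the role of baseline.** The protocol does not say how the baseline score enters. If it is a free response level and the arm contrast is change at one follow-up, the variance relative to covariate adjustment is 2(1 − ρ)/(1 − ρ²) = 2/(1 + ρ). That is 1.54, 1.33 and 1.18 at assumed correlations of 0.3, 0.5 and 0.7. Under randomisation this is lost precision, not bias.

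**The case against.** **Detail belongs in a SAP.** No SAP is shown. Link function, covariates and the choice between GEE and random effects are usually settled there. Promising odds ratios shows that a binary analysis is intended. Effect sizes stand under their own label, and Cohen's d is not an ANOVA coefficient either, so the text need not mean that effect sizes are read off the ANOVA. Much of this stands, and silence on such detail is no fault. What remains is that the protocol is not silent: it assigns one model to all primary and secondary outcomes, and that model does not fit some of them.

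**The trial is built on the scores.** The sample size uses PCL-5 means, for which the named model is suitable. This stands, and the model should be kept there.

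**Stronger readings that the documents do not support.**

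- A reader might infer that ANOVA on 0/1 data makes the tests invalid or raises the false-positive rate. A linear model for proportions is a defensible way to compare arms; the mismatch lies in the effect measure and its interval.
- A reader might infer that the reported odds-ratio intervals will be too wide by some known amount. The protocol does not say that odds ratios would be derived from the ANOVA, and it gives no loss rate, so no such amount follows.
- A reader might infer that the diagnosis outcome can be analysed only in those diagnosed at entry. That is true of loss, but the Measures text also says existence, which at follow-up is defined for every randomised participant.
- A reader might infer that leaving the role of baseline open biases the score comparison. It affects precision only.

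**Conclusion.** The point holds as a mismatch inside the plan. The only model named for Study 1 outcomes does not estimate the odds ratios with 95% CIs that the same paragraph promises for the yes/no measures, one of them primary. Confidence in this reading of the text is high.

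The size cannot be fixed from the documents. The odds ratios of 2.25 and 3.86 for one 20-point difference rest on assumed loss rates. The spread from 2.25 to 3.80 for one result rests also on assumed random-intercept SDs, with no covariates. These figures show that the model must be chosen in advance; they do not forecast an error in the results. The change should be made, though the planned analysis of the scores remains sound without it.

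**What to change.** 1. **Scores.** Limit the linear mixed model to the PCL-5, PHQ-9 and GAD-7 scores. Enter the baseline score as a covariate, or constrain the arm means to be equal at baseline, and include setting. This gains precision at no cost in data; it does not correct a bias.
2. **Yes/no outcomes at post-treatment visits.** Name one model: a logistic mixed model with a participant random intercept and terms for arm, visit, arm-by-visit, setting and the relevant baseline score, fitted by maximum likelihood, in line with the MAR assumption already stated. Report odds ratios with 95% CIs, label them subject-specific, and give model-standardised proportions by arm beside them.
3. **Diagnosis.** Analyse existence of PTSD diagnosis at follow-up in all randomised participants. Add loss of diagnosis among those diagnosed at entry as a supporting analysis. State the visit(s) at which the diagnosis is read.

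**Cost.** A few lines of analysis text; baseline scores and setting codes are already collected. Two practical points follow. The model needs participant-level records linked across visits, while Section 2 describes transfer to the analysing university in anonymised and aggregated form, so the anonymised transfer must keep rows linked by participant. Also, Section 6 lists only the three scales for follow-up assessment and Section 4 takes the diagnosis from medical records, so the professional-confirmed reading that the Measures text already intends must actually be recorded at the chosen visit(s). If it is not yet scheduled there, that is more work than adding a data field.

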
Pseudonymisation and Coding Strategy will be based on the European Data Protection Board (EDPB) Guidelines on Pseudonymisation, 2025.

The study design requires pseudonymisation only for follow-up post-treatment assessments for PTSD symptoms severity (PCL-5), existence and severity of depression (PHQ-9), and anxiety-related (GAD-7) symptoms at 2 weeks, 6 months, and 12 months post-treatment. The main purpose is to enable linkage of repeated assessments while restricting direct identification.

It is planned to have 3 experimental groups in 3 different treatment settings (Hospital Inpatient, Hospital Outpatient, Psychotherapeutic Practice) and 3 control groups with "treatment-as-usual" in the same three types of settings, with 20 participants each. It creates 6 study samples with 120 participants in total. Each participant will receive a unique study participant ID (PID) upon inclusion, generated as: [GroupCode]- [SettingCode]- [SequentialNumber]. For example, ExpHIP001: Experimental group, Hospital Inpatient setting, Participant 1.

Enrolment and randomisation (steps taken at baseline and immediately after each enrolment). As soon as a participant is enrolled, the site coordinator assigns a sequential number, allocates the study sample using Randomisation Software, and creates a PID. The coordinator writes down the PID on each paper document for follow-up contact and records the PID on the pseudonymization key list uploaded to the NPA/ RCFG staff laptop/desktop (encrypted hard drives).

Data collection (before and during follow-up assessments). Whenever data are gathered later, the research staff involved (therapists, assessors, or other professionals) manually write each participant's PID on every paper document related to that follow-up contact, allowing the data to be linked back to the correct person without revealing their identity.

For the follow-up post-treatment assessments (2 weeks / 6 months / 12 months), sites' coordinators will use the secure key to retrieve participant contact from the PID. Re-assessment tools will be administered with the same PID. Results will be stored again using a pseudonym only.

Study 2: The RTM Protocol and Training Feasibility Study

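### The Study 1 analysis names no baseline covariate, setting term or arm-by-setting term, so it leaves avoidable imprecision in the arm comparison and gives no estimate for Objective 2

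*Protocol*

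**What the plan says.** The whole inferential plan for Study 1 is one line in Section 4, Methodology: "Primary and Secondary Outcome Analysis: mixed-effects repeated measures ANOVA". It lists no fixed effects, covariates or interactions. Baseline appears in that paragraph only as "baseline comparability between groups", checked by t-tests and chi-square tests.

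Section 4 gives four measurement times: "Data collection will occur at baseline (diagnostic session), 1 month after complete treatment application, in 6 months (follow-up booster session", and then 12 months. At these times "scores from PCL-5 (for PTSD), PHQ-9 (for depression), GAD-7 (for anxiety) diagnostic scales will be collected". The primary outcome is "MH professional proved existence or loss of PTSD diagnosis and/or PTSD symptoms severity measured by PTSD Checklist PCL-5", so it has a binary and a continuous component.

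Section 6 (Study 1, pseudonymisation and coding) plans "3 experimental groups in 3 different treatment settings (Hospital Inpatient, Hospital Outpatient, Psychotherapeutic Practice", with matching control samples of 20 each, 120 in total. The setting is coded in every participant ID. Objective 2 in Section 2 concerns effectiveness across "inpatient and outpatient hospital care for veterans and private psychotherapy for civilians".

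**The concern.** Read in the usual way, a repeated measures ANOVA over these four times treats baseline PCL-5 as one level of the outcome. The group main effect then averages in a visit at which randomisation makes the expected difference zero. The group-by-time test spreads a sustained effect over 3 degrees of freedom. A change contrast carries the full noise of the baseline score. The baseline t-tests and chi-square tests add nothing to the treatment estimate.

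Setting defines the six samples but does not appear in the analysis. Two things are at stake: precision for the arm comparison, and any answer to Objective 2, for which the protocol states no estimate, contrast or interaction.

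**Working it through.** **The protocol's own figure.** Inputs from Section 4: difference 25.0 − 21.0 = 4, SD 3.0, two-sided 5%, power 80%, dropout 20%. Per group, n = 2(1.960 + 0.842)² × 3² / 4² = 8.83, so 9. After dropout, 9/0.8 = 11.25, so 12. The stated 12 reproduces. It is a plain two-sample comparison, using neither baseline nor setting.

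**Baseline.** Assumptions: equal variance at all visits, one correlation r between any two visits (compound symmetry), and a constant effect d (in SD) at all three follow-ups. The documents do not give r, so a range is shown. In SD² units, up to the common factor 2/n:

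- mean follow-up minus baseline: V₁ = (1 + 2r)/3 + 1 − 2r
- baseline-adjusted mean follow-up: V₂ = (1 + 2r)/3 − r²

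| r | V₁ | V₂ | reduction 1 − V₂/V₁ |
|---|---|---|---|
| 0.3 | 0.933 | 0.443 | 52.5% |
| 0.5 | 0.667 | 0.417 | 37.5% |
| 0.7 | 0.400 | 0.310 | 22.5% |

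The unadjusted mean of the follow-ups has variance (1 + 2r)/3 = 0.533, 0.667, 0.800. It beats the change contrast at r = 0.3 and loses to it at 0.7. V₂ is below both at every r shown.

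**Power.** Evaluable per arm: 60 × 0.8 = 48. Noncentrality is (48/2)d²/V. With an illustrative d = 0.4 (assumed), this is 3.84/V. Normal approximation, two-sided 5%:

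| r | change contrast | baseline-adjusted mean |
|---|---|---|
| 0.3 | 53% | 84% |
| 0.5 | 67% | 86% |
| 0.7 | 87% | 94% |

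With the protocol's own effect, d = 4/3 = 1.33, (48/2)d² = 42.7. Even the largest variance above (0.933) gives noncentrality 45.7, so power exceeds 99.9% with either analysis.

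**Setting.** If allocation is balanced within setting and setting explains a share R² of the variance (assumed), leaving it out inflates the standard error of a between-participant contrast by 1/√(1 − R²). That is 1/√0.9 = 1.054 and 1/√0.8 = 1.118, or about 5% and 12%. The true two-sided error rate falls from 0.050 to about 0.039 and 0.028.

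**Objective 2.** Detectable differences at 80% power, with 20 per cell (16 after 20% dropout), from a single unadjusted comparison:

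- within one setting: 2.802 × √(2/20) = 0.89 SD (√(2/16): 0.99 SD)
- difference in effect between two settings: 2.802 × √(4/20) = 1.25 SD (√(4/16): 1.40 SD)

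At SD 3 the second line is 3.8 (4.2) points, about as large as the whole assumed effect of 4.

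**The case against.** The strongest reply is that silence is not exclusion. The line names a class of model without even listing arm or time, and covariate lists usually belong in a statistical analysis plan, which is not shown. It stands to this extent: the text does not rule out adjustment. But the protocol does name a method, and the only role it gives baseline outside the repeated outcome is a comparability check.

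A reader might infer that baseline is ignored. The documents do not support that: in a repeated measures model baseline is already a response. A mixed model constrained to a common baseline mean would recover essentially the efficiency of covariate adjustment, but the protocol does not specify one.

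A reader might also set the least favourable tests against the adjusted analysis. At d = 0.4 and r = 0.5, power is about 46% for the group main effect and 50% for the 3-df group-by-time test, against 86%. Much of that gap comes from the choice of contrast, and the protocol commits to neither test. The fair comparison is with a 1-df contrast, as above.

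On setting, a setting effect that is constant over time cancels from a within-participant contrast, so the 5–12% applies only to between-participant comparisons. It shrinks once baseline is adjusted for, and should not be added to the baseline gain. Allocation within setting is implied by the six samples of 20 but is never stated as stratified.

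Finally, under the protocol's own effect size nothing is lost in practice. That is correct.

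None of these replies supplies an analysis for Objective 2.

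**Conclusion.** The point holds as an improvement to the stated analysis, and as a gap for Objective 2; it is not an error in a stated figure. Naming baseline adjustment would cut the variance of the change contrast by roughly a fifth to a half (22.5% to 52.5% for r from 0.7 down to 0.3, compound symmetry assumed). The gain matters only if the true effect is smaller or the SD larger than 4 points with SD 3. The setting term is worth about 5–12% of a between-participant standard error, conditional on balanced allocation within setting and an assumed R² of 10–20%.

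The Objective 2 gap rests on no assumption: a stated objective and a six-sample layout have no by-setting estimate attached. A reader might expect the missing analysis to show where RTM works best. It cannot do so reliably with 16–20 per cell. Moreover, hospital versus private setting is also veteran versus civilian, so no difference across that line can be attributed to setting.

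**What to change.** In Section 4, Study 1, replace the analysis line with the following:

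- **PCL-5:** a linear mixed model for the post-baseline scores, with baseline PCL-5 as covariate and fixed effects for arm, visit, arm-by-visit and setting. Name one primary 1-df contrast, for example the arm difference averaged over the follow-ups; without that, the precision shown above is not secured.
- **PHQ-9 and GAD-7:** the same form, each with its own baseline score.
- **Loss of diagnosis:** a logistic model with arm, setting and baseline PCL-5.
- **Objective 2:** add arm-by-setting and report the three within-setting RTM-minus-control contrasts with 95% confidence intervals. Label them exploratory and state the veteran/civilian overlap.
- **Baseline tables:** descriptive, without tests.

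Section 6 should also say whether allocation is stratified by setting. The cost is a few sentences, with no new data, visits or participants. The change should be made before outcome data are seen.
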